### 6.3 Dose modifications

#### 6.3.1 Dose modification and dose delay

For patients who do not tolerate the protocol-specified dosing schedule, dose adjustments are permitted in order to allow the patients to continue the study treatment. Any changes in LDK378 administration must be recorded on the Dosage Administration Record eCRF.

Patients whose treatment is interrupted or permanently discontinued due to an AE must be followed until resolution or stabilization of the event. Patients requiring interruptions greater than 2 cycles (42 days) will be discontinued from study treatment. In certain cases, if the Investigator and the Sponsor conclude that a patient, who has experienced a treatment

interruption greater than 2 cycles (42 days), could benefit from additional treatment, continuation may be allowed.

LDK378 dose reduction will follow the dose reduction steps described in [Table 6-3](#). For each patient, a maximum of 3 dose modifications will be allowed after which the patient must be discontinued from treatment with LDK378. Once the dose of LDK378 has been reduced, it cannot be re-escalated. If a patient continues treatment with LDK378 after RECIST-defined PD confirmed by the investigator, the criteria for dose modification will also apply.

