### 6.2.4 Definitions of dose limiting toxicities (DLTs)

A DLT is defined as an adverse event or abnormal laboratory value assessed as unrelated to disease, disease progression, inter-current illness, or concomitant therapies that occurs within the first 21 days (Cycle 1) of treatment with LDK378 and meets any of the criteria included in [Table 6-2](#). Any adverse event is not considered a DLT if it does not happen within the first 21 days of treatment. However, medically significant events should be followed up as for DLTs. NCI CTCAE version 4.03 will be used for all grading. For the purpose of dose-escalation decisions, DLTs will be considered and included in the BLRM.

The investigator must notify Novartis immediately of any unexpected CTCAE grade  $\geq 3$  adverse events or laboratory abnormalities. Prior to enrolling patients into a higher dose level, CTCAE grade  $\geq 2$  adverse events will be reviewed for all patients at the current dose level

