## Dose modification related to DLTs

If a patient experiences a DLT, treatment with LDK378 should be held. Following resolution of the toxicity to grade 1 or to the patient's baseline value the patient may resume treatment with LDK378. In general patients who resume therapy following a DLT should resume at a lower dose level assessed to be safe with a minimum dose reduction of 50 mg. However, following recovery of a DLT that was not considered clinically important or can be managed if it recurs (e.g., replacement of an electrolyte), the patient may resume therapy without dose reduction, if the investigator considers that to be in the best interest of the patient. The dose should not be reduced below 150 mg/m^2. Provisional dose levels for LDK378 are listed in [Table 6-1](#).

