**Table 6-3 Dose reduction steps for LDK378 at RDE (fasted and fed states)**

| LDK378 dose levels  | Dose* and schedule                             |
|---------------------|--|
| Starting dose level | RDE: 500/510 mg/m  QD continuously |
| Dose level -1       | 400 mg/m  QD continuously          |
| Dose level - 2      | 300 mg/m  QD continuously          |
| Dose level -3       | 200 mg/m  QD continuously          |

\*Dose reduction should be based on the worst preceding toxicity as per NCI-CTCAE version 4.03

\*\*Dose reduction below 200 mg/m^2/day is not allowed. If a dose reduction below 200 mg/m^2/day is required, the patient should be permanently discontinued from LDK378

Guidelines for dose interruptions and re-initiation of LDK378 treatment (with or without dose reduction) are described in [Table 6-4](#).

Patients, who discontinue from the study for a study-related adverse event or an abnormal laboratory value, must be followed as described in [Section 7.1.3](#).

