**General guidelines for dose modifications for toxicities other than those listed in [Table 6-4](#):**

For grade 1 and tolerable grade 2 treatment-related toxicities, patients are encouraged to continue at the current dose of study treatment. For intolerable grade 2 treatment-related toxicities, dosing should be interrupted until resolution to grade 1 or lower followed by dose reduction to the next dose level.

For grade 3 or grade 4 treatment-related toxicity that is not considered by the Investigator to be life-threatening, patients should interrupt study treatment until resolution of that toxicity, to grade 1 or lower. Study treatment may be resumed following a dose reduction to the next dose level if, in the opinion of the Investigator, the patient continues to experience clinical benefit. For any grade 3 or grade 4 treatment-related toxicity that is considered by the Investigator to be life-threatening, study treatment must be permanently discontinued.

In the case of a DLT of QTc prolongation (QTc >500 ms) LDK378 must be withheld until resolution to grade 1 or less. If LDK378 is resumed, the dose must be reduced by at least 1 dose level and at least 50 mg. In the case of grade 4 QTc prolongation (QTc >500 ms complicated by Torsades de pointes, polymorphic ventricular tachycardia, or signs/symptoms of serious arrhythmia; or >60 ms change from baseline complicated by Torsades de pointes, polymorphic ventricular tachycardia, or signs/symptoms of serious arrhythmia) LDK378 should be permanently discontinued.

Patients whose treatment is interrupted or permanently discontinued due to an AE must be followed until resolution or stabilization of the event. Patients requiring interruptions greater

[figure not shown]

than 2 cycles (42 days) will be discontinued from study treatment. In certain cases, if the Investigator and the Sponsor conclude that a patient, who has experienced a treatment interruption greater than 2 cycles (42 days), could benefit from additional treatment, continuation may be allowed.

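### Minor: outside the DLT and QTc rules, a one-level dose reduction has no mg minimum, so for BSA 0.375 to <0.45 m² one of the three Table 6-3 steps leaves the administered dose unchanged

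*Protocol*

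**What the plan says.** - **Dose calculation.** Protocol Section 6.1.1: level (mg/m²) times BSA, rounded to the nearest 50 mg, with a 50 mg minimum dose. Section 5.3, item 4, excludes only BSA below 0.35 m².
- **Reduction steps.** Section 6.3.1: "LDK378 dose reduction will follow the dose reduction steps described in" Table 6-3, which lists 500/510, 400, 300 and 200 mg/m². If a dose below the 200 mg/m² floor "is required, the patient should be permanently discontinued from LDK378".
- **Cap.** Section 6.3.1: "For each patient, a maximum of 3 dose modifications will be allowed after which the patient must be discontinued from treatment with LDK378".
- **After a DLT.** Section 6.2.4: patients in general "should resume at a lower dose level assessed to be safe with a minimum dose reduction of 50 mg". The same section limits what a DLT is: "Any adverse event is not considered a DLT if it does not happen within the first 21 days of treatment". It adds: "However, medically significant events should be followed up as for DLTs".
- **QTc above 500 ms.** General guidelines in Section 6.3.1: "If LDK378 is resumed, the dose must be reduced by at least 1 dose level and at least 50 mg".
- **All other toxicities.** Table 6-4 and the general guidelines ask for a reduction of one dose level, or to the next level, and give no mg amount.

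**The concern.** A reduction is ordered so that the child takes less drug. Table 6-3 steps are 100 mg/m² (110 for the first step from 510), so below 0.5 m² a step is worth less than 50 mg, and two neighbouring levels can round to the same mg dose. For DLTs the protocol prevents this with its 50 mg minimum. After day 21 no event is a DLT, and following up a medically significant event as for a DLT does not set a mg amount.

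The triggers are not rare. In adults at 750 mg (Section 1.2.1.2.1), 26.7% had grade 3-4 ALT increase and 58.4% had a dose reduction for an adverse event. Of all patients 38.8% had only one, so 58.4 − 38.8 = 19.6% had more than one. In Table 6-4, grade 3 or 4 ALT or AST without the bilirubin elevation calls for one level down. At stake is a very small child restarting on the mg dose at which the toxicity occurred. As background only, the Amendment 2 rationale shows that the sponsor knew rounding could cancel a reduction at low BSA.

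**Working it through.** The plan gives no figure of its own for this point.

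**Inputs.** Levels 500 or 510, 400, 300, 200 mg/m² (Table 6-3); rounding to the nearest 50 mg (Section 6.1.1); BSA from 0.35 m² (Section 5.3).

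**Rule.** A step from level a to level b is null when a × BSA and b × BSA round to the same multiple of 50. A level L rounds to dose D when (D − 25)/L ≤ BSA < (D + 25)/L, with ties rounded up.

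**Null zones within the eligible range**

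- 300 to 200, both 100 mg: the 200 level needs BSA ≥ 75/200 = 0.375 and the 300 level needs BSA < 125/300 = 0.4167.
- 400 to 300, both 150 mg: BSA ≥ 125/300 = 0.4167 and < 175/400 = 0.4375.
- 500 to 400, both 200 mg: BSA ≥ 175/400 = 0.4375 and < 225/500 = 0.45.
- 510 to 400, both 200 mg: BSA ≥ 0.4375 and < 225/510 = 0.4412.

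The zones adjoin without overlap, so exactly one step is null across 0.375 to <0.45 m² (500 start) or 0.375 to <0.441 m² (510 start). From 0.5 m² a step is at least 50 mg and cannot vanish. A run over 0.35 to 2.20 m² in steps of 0.00005 found no null step elsewhere.

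| BSA (m²), 500 start | Doses in mg at start / −1 / −2 / −3 | Null step |
|---|---|---|
| 0.35 to <0.375 | 200 / 150 / 100 / 50 | none |
| 0.375 to <0.4167 | 200 / 150 / 100 / 100 | 300 to 200 |
| 0.4167 to <0.4375 | 200 / 150 / 150 / 100 | 400 to 300 |
| 0.4375 to <0.45 | 200 / 200 / 150 / 100 | 500 to 400 |
| 0.45 to 0.50 | 250 / 200 / 150 / 100 | none |

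Rounding ties down changes only isolated points: exactly 0.375 m² then has no null step, and exactly 0.45 and exactly 0.35 m² each gain one at the 500 start.

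**Effect of the proposed rule.** Skipping to the next level that lowers the dose gives 200 / 150 / 100 mg and then discontinuation at every BSA in the band. There, 100 mg is 100/0.45 = 222 to 100/0.375 = 267 mg/m², above the 200 floor. A bare 50 mg minimum would instead lead to 50 mg, that is 50/0.45 = 111 to 50/0.375 = 133 mg/m², below the floor.

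**The case against.** **Literal reading.** The protocol speaks of dose reduction, and a site that computes the same mg dose has reduced nothing. A careful investigator would notice. That is fair, but the text does not say what to do next (stay, skip a level or stop), so sites may differ.

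**Does a null step use up a modification?** A reader might infer that it counts towards the cap of three. Section 6.3.1 does not say so. SAP Section 5.3 bases dose changes on the CRF check box and the dose actually taken, and defines a change as a difference between dosing records. That points the other way, though it is an analysis definition. What remains is that Table 6-3 offers three levels below the start and a null step consumes one.

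**Is the third step usually the one lost?** A reader might infer this because the 300-to-200 zone is the widest. Zone width is not patient share, and the documents give no BSA distribution. The youngest possible remaining patient was 12 months at entry by 31 October 2017, plus 199 days to 18 May 2018, about 18.5 months. Assuming 8.5-11 kg and 76-82 cm at that age (not in the documents), the square-root formula gives 0.42-0.50 m², which would leave that zone empty.

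**QTc.** The grade 3 QTc row of Table 6-4 may already be covered by the 50 mg rule in the general guidelines, so it should not be counted as unprotected.

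**Proportion.** Enrolment is closed, doses are recalculated as BSA changes, benefiting patients move to other access, and the most dangerous toxicities lead to discontinuation. The protocol also accepts unchanged restarts in places, such as after a DLT judged not clinically important. All of this stands and keeps the point small. Those restarts are deliberate, however, whereas here the plan orders a reduction and rounding cancels it.

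**Conclusion.** The point holds as a minor patient-safety improvement. Outside the DLT rule and the QTc rule, one-level reductions have no mg minimum, and exactly one of the three Table 6-3 steps is null for BSA 0.375 to <0.45 m² (500 start) or to <0.441 m² (510 start).

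This rests on rounding to the nearest 50 mg, the nominal levels of Table 6-3, and BSA held constant between steps. How many patients are affected, and which step they would lose, cannot be determined. At most the twelve patients on treatment at Amendment 8 are in question, and possibly none.

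A reader might infer a threat to the MTD or to the DLT endpoint. The documents do not support that, because DLTs are cycle 1 events and reductions after them carry the 50 mg minimum.

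**What to change.** Add to Tables 6-3 and 6-4:

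> Any dose-level reduction, for any toxicity and in any cycle, must lower the administered daily dose by at least 50 mg. If the next level rounds to the same mg dose, go to the next lower Table 6-3 level that lowers it; this counts as one modification. If there is none, discontinue LDK378. The 200 mg/m² floor applies to the nominal level.

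The floor must be nominal. Applied to the administered dose, it would disable level −3 for many larger children: at 0.60 m², 200 × 0.60 = 120 mg rounds to 100 mg, or 167 mg/m².

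Under Section 12.1 this needs a written amendment with sponsor and ethics approval, and health authority approval where required; it adds no visits or data. If no further amendment is planned, put the rule in the rollover protocol foreseen in Section 4.3.

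The clinical price is that patients in the band have two usable reductions, so a third toxicity needing one means discontinuation. At 0.375 to <0.4167 m² that replaces continuing on an unchanged 100 mg and could stop a child who is benefiting. Ladders outside the band do not change. The different floor in Section 6.2.4 ("The dose should not be reduced below 150 mg/m"²) is a separate matter and is not part of this change.

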**Table 6-3 Dose reduction steps for LDK378 at RDE (fasted and fed states)**

| LDK378 dose levels  | Dose* and schedule                             |
|---------------------|--|
| Starting dose level | RDE: 500/510 mg/m  QD continuously |
| Dose level -1       | 400 mg/m  QD continuously          |
| Dose level - 2      | 300 mg/m  QD continuously          |
| Dose level -3       | 200 mg/m  QD continuously          |

\*Dose reduction should be based on the worst preceding toxicity as per NCI-CTCAE version 4.03

\*\*Dose reduction below 200 mg/m^2/day is not allowed. If a dose reduction below 200 mg/m^2/day is required, the patient should be permanently discontinued from LDK378

Guidelines for dose interruptions and re-initiation of LDK378 treatment (with or without dose reduction) are described in [Table 6-4](#).

Patients, who discontinue from the study for a study-related adverse event or an abnormal laboratory value, must be followed as described in [Section 7.1.3](#).

**General guidelines for dose modifications for toxicities other than those listed in [Table 6-4](#):**

For grade 1 and tolerable grade 2 treatment-related toxicities, patients are encouraged to continue at the current dose of study treatment. For intolerable grade 2 treatment-related toxicities, dosing should be interrupted until resolution to grade 1 or lower followed by dose reduction to the next dose level.

For grade 3 or grade 4 treatment-related toxicity that is not considered by the Investigator to be life-threatening, patients should interrupt study treatment until resolution of that toxicity, to grade 1 or lower. Study treatment may be resumed following a dose reduction to the next dose level if, in the opinion of the Investigator, the patient continues to experience clinical benefit. For any grade 3 or grade 4 treatment-related toxicity that is considered by the Investigator to be life-threatening, study treatment must be permanently discontinued.

In the case of a DLT of QTc prolongation (QTc >500 ms) LDK378 must be withheld until resolution to grade 1 or less. If LDK378 is resumed, the dose must be reduced by at least 1 dose level and at least 50 mg. In the case of grade 4 QTc prolongation (QTc >500 ms complicated by Torsades de pointes, polymorphic ventricular tachycardia, or signs/symptoms of serious arrhythmia; or >60 ms change from baseline complicated by Torsades de pointes, polymorphic ventricular tachycardia, or signs/symptoms of serious arrhythmia) LDK378 should be permanently discontinued.

Patients whose treatment is interrupted or permanently discontinued due to an AE must be followed until resolution or stabilization of the event. Patients requiring interruptions greater

[figure not shown]

than 2 cycles (42 days) will be discontinued from study treatment. In certain cases, if the Investigator and the Sponsor conclude that a patient, who has experienced a treatment interruption greater than 2 cycles (42 days), could benefit from additional treatment, continuation may be allowed.

**Table 6-4 Criteria for interruption and re-initiation of LDK378 treatment**

| Worst toxicity (CTCAE 4.03 Grade)*  | Dose Modifications for LDK378   |
|--|--|
| HEMATOLOGICAL   |  |
| Neutropenia (ANC)   |  |
| Grade 1 (ANC < LLN - $1.5 \times 10^9/L$ )
Grade 2 (ANC < 1.5 and $\geq 1.0 \times 10^9/L$ )
Grade 3 (ANC < 1.0 and $\geq 0.5 \times 10^9/L$ )                       | Maintain dose level  |
| Grade 4 (ANC < $0.5 \times 10^9/L$ )   | Omit dose until resolved to $\leq$ Grade 2, then:
If resolved in $\leq 7$ days, then maintain dose level
If resolved in $> 7$ days, then $\downarrow 1$ dose level |
| Febrile neutropenia
(ANC < $1.0 \times 10^9/L$ , with a single temperature of $\geq 38.3$ °C or a sustained temperature of $\geq 38$ °C for more than one hour ) | Omit dose until clinically resolved and neutropenia $\leq$ Grade 2, then $\downarrow 1$ dose level   |
| Thrombocytopenia  |  |
| Grade 1 (PLT < LLN - $75 \times 10^9/L$ )
Grade 2 (PLT < 75 and $\geq 50 \times 10^9/L$ )   | Maintain dose level  |
| Grade 3 (PLT < 50 and $\geq 25 \times 10^9/L$ )  | Omit dose until resolved to $\leq$ Grade 2, then:
If resolved in $\leq 7$ days, then maintain dose level
If resolved in $> 7$ days, then $\downarrow 1$ dose level |
| Grade 4 (PLT < $25 \times 10^9/L$ )  | Omit dose until resolved to $\leq$ Grade 2, then $\downarrow 1$ dose level   |
| HEPATIC   |  |
| Alkaline phosphatase and/or Gamma-glutamyl transpeptidase (GGT)   |  |
| Isolated elevations of any grade   | Maintain dose level  |
| Total Bilirubin**
(for patients with Gilbert Syndrome these dose modifications apply to changes in direct [conjugated] bilirubin only)                           |  |
| Grade 1 ( $> ULN$ and $\leq 1.5 \times ULN$ )  | Maintain dose level with liver function test (LFTs)*** monitored as per protocol   |

| Worst toxicity (CTCAE 4.03 Grade)*   | Dose Modifications for LDK378  |
|---|---|
| Grade 2 (> 1.5 and ≤ 3.0 x ULN) with ALT or AST ≤ 3.0 x ULN   | Omit dose until resolved to ≤ Grade 1, then:
If resolved in ≤ 7 days, then maintain dose level
If resolved in > 7 days, then ↓ 1 dose level   |
| Grade 3 (> 3.0 and ≤ 10.0 x ULN) with ALT or AST ≤ 3.0 x ULN  | Omit dose until resolved to ≤ Grade 1, then:
If resolved in ≤ 7 days, ↓ 1 dose level
If resolved in > 7 days, discontinue patient from LDK378 |
| Grade 4 (> 10.0 x ULN)  | Permanently discontinue patient from LDK378   |
| AST or ALT   |   |
| Grade 1 (> ULN and ≤ 3.0 x ULN)   | Maintain dose level with LFTs*** monitored per protocol   |
| Grade 2 (> 3.0 and ≤ 5.0 x ULN) without total bilirubin elevation to > 2.0 x ULN  | Maintain dose level with LFTs*** monitored per protocol   |
| Grade 3 (> 5.0 and ≤ 20.0 x ULN) without total bilirubin elevation to > 2.0 x ULN   | Omit dose until resolved to ≤ Grade 1, then ↓ 1 dose level  |
| Grade 4 (> 20.0 x ULN) without total bilirubin elevation to > 2.0 x ULN   | Omit dose until resolved to ≤ Grade 1, then ↓ 1 dose level  |
| AST or ALT and concurrent Total bilirubin  |   |
| AST or ALT > 3.0 x ULN with total bilirubin > 2.0 x ULN in the absence of cholestasis or hemolysis  | Permanently discontinue patient from LDK378. Refer to Section 6.3.2.2 for additional follow-up.                                     |
| AST or ALT > 5.0 and ≤ 20.0 x ULN with total bilirubin > 1.5 and ≤ 3.0 x ULN  | Permanently discontinue patient from LDK378 if event reoccurs after dose reduction.   |
| PANCREATIC   |   |
| Amylase and/or lipase evaluations (in absence of clinical symptoms)   |   |
| Grade 1 (> ULN and ≤ 1.5 x ULN)   | Maintain dose level   |
| Grade 2 (> 1.5 - 2.0 x ULN)   | Maintain dose level   |
| Grade ≥ 3 (> 2.0 x ULN)   | Omit dose until resolved to ≤ Grade 1, then ↓ 1 dose level  |
| Note: Withhold LDK378 for acute onset of new or progressive unexplained abdominal symptoms, such as severe pain or vomiting; perform diagnostic procedures (e.g., abdominal CT scan or ultrasound) to exclude pancreatic pathology. |   |
| RENAL  |   |

| Worst toxicity (CTCAE 4.03 Grade)*               | Dose Modifications for LDK378  |
|---|---|
| Serum creatinine                                 |   |
| Grade 1 (>1 and ≤1.5 x baseline; >ULN and ≤ 1.5 x ULN)  | Maintain dose level   |
| Grade 2 (>1.5 and ≤3.0 x baseline; > 1.5 and ≤ 3 x ULN) | Omit dose until resolved to ≤ Grade 1, then:
If resolved in ≤ 7 days, then maintain dose level
If resolved in > 7 days, then ↓ 1 dose level                         |
| Grade 3 (>3.0 x baseline; > 3.0 and ≤ 6.0 x ULN)        | Omit dose until resolved to ≤ Grade 1, then ↓ 1 dose level  |
| Grade 4 (> 6.0 x ULN)                                   | Permanently discontinue patient from LDK378   |
| GASTROINTESTINAL                                 |   |
| Diarrhea****                                     |   |
| Grade 1   | Maintain dose level but adjust anti-diarrhea treatment  |
| Grade 2 (despite maximal anti-diarrheal medication)     | Omit dose until resolved to ≤ Grade 1, then maintain dose level.
If diarrhea returns as ≥ Grade 2, then omit dose until resolved to ≤ Grade 1, then ↓ 1 dose level     |
| Grade 3 (despite maximal anti-diarrheal medication)     | Omit dose until resolved to ≤ Grade 1, then ↓ 1 dose level  |
| Grade 4 (despite maximal anti-diarrheal medication)     | Omit dose until resolved to ≤ Grade 1, then ↓ 1 dose level  |
| Nausea*****                                      |   |
| Grade 1 or 2  | Maintain dose level but adjust anti-emetic treatment  |
| Grade 3 (despite standard anti-emetics)                 | Omit dose until resolved to ≤ Grade 1, then ↓ 1 dose level  |
| Vomiting*****                                    |   |
| Grade 1   | Maintain dose level but adjust anti-emetic treatment  |
| Grade 2 (despite standard anti-emetics)                 | Omit dose until resolved to ≤ Grade 1, then maintain dose level.
If vomiting returns as ≥ Grade 2, then suspend dose until resolved to ≤ Grade 1, then ↓ 1 dose level. |
| Grade 3 (despite standard anti-emetics)                 | Omit dose until resolved to ≤ Grade 1, then ↓ 1 dose level  |
| Grade 4 (despite standard anti-emetics)                 | Omit dose until resolved to ≤ Grade 1, then ↓ 1 dose level  |
| METABOLIC  |   |
| Any Grade hypophosphatemia                       | Treatment with phosphate supplements as clinically indicated and maintain dose level  |

| Worst toxicity (CTCAE 4.03 Grade)*   | Dose Modifications for LDK378  |
|---|---|
| Persistent hyperglycemia (glucose > 250 mg/dL) despite optimal anti-hyperglycemic therapy  | Omit dose until hyperglycemia is adequately controlled then resume LDK378 at ↓ 1 dose level
If adequate hyperglycemic control cannot be achieved with optimal medical management permanently discontinue patient from LDK378 |
| GENERAL DISORDERS  |   |
| Fatigue (asthenia)   |   |
| Grade 1 or 2  | Maintain dose level   |
| Grade 3   | If grade 3 fatigue resolves to Grade 2 in ≤ 7 days, maintain dose level
If grade 3 fatigue lasts > 7 days, omit dose until resolved to ≤ Grade 2 and then ↓ dose level   |
| PULMONARY  |   |
| Notes:  |   |
| 
 
Withhold LDK378 for acute onset of new or progressive unexplained pulmonary symptoms, such as dyspnea, cough and fever and during diagnostic workup for pneumonitis/ILD.
 
During evaluation of potential grade 2, 3, and 4 pneumonitis, if an infectious etiology is confirmed (i.e., pneumonia) and pneumonitis is excluded, then consider resuming LDK378 at current dose level after the pneumonia resolves.
 
For pneumonitis not treatment related: If pneumonitis/ILD of grade 2 or worse is confirmed, study drug should be permanently discontinued. If Grade 1 resolves within 6 weeks, LDK378 may be resumed reduced by 1 dose level, otherwise it must be discontinued. If grade 1 pneumonitis recurs after dose reduction, then LDK378 must be permanently discontinued.
 
 |   |
| PNEUMONITIS  |   |
| Any Grade treatment-related ILD/pneumonitis   | Permanently discontinue patient from LDK378   |
| CARDIAC  |   |
| Electrocardiogram QT corrected (QTc) interval prolonged  |   |
| Grade 1 (QTc 450-480 ms)
Grade 2 (QTc 481-500 ms)  | Maintain dose level   |

| Worst toxicity (CTCAE 4.03 Grade)*   | Dose Modifications for LDK378  |
|---|---|
| Grade 3 (QTc $\geq$ 501 ms on at least two separate ECGs)   | 
Omit dose until QTc is less than 481 ms , then <math>\downarrow</math> 1 dose level
                     - Assess the quality of the ECG recording and the QT value and repeat if needed
 
Repeat ECG in 24 hours, or less, as clinically indicated; continue monitoring as clinically indicated until QTc < 481 ms.
 
In addition:-Determine the serum electrolyte levels (in particular hypokalemia, hypomagnesemia). If abnormal, correct abnormalities before resuming study drug treatment
 
- Review concomitant medication use for drugs with the potential to increase the risk of drug exposure related to QT prolongation
 
After resumption of dosing:
                     - Repeat ECGs 7 days after dose resumption for all patients who had therapy interrupted due to QTc <math>\geq</math> 501 ms.
 |
| Grade 4 (QTc $\geq$ 501 or > 60 ms change from baseline and Torsades de pointes or polymorphic ventricular tachycardia or signs/symptoms of serious arrhythmia) | Permanently discontinue patient from LDK378   |
| BRADYCARDIA  |   |
| Grade 1 or Grade 2  | Omit dose until recovery to asymptomatic bradycardia or to a heart rate $\geq$ 60 bpm
Evaluate concomitant medications known to cause bradycardia and adjust the dose of LDK378  |
| Grade 3   | Omit dose until recovery to asymptomatic bradycardia or to a heart rate $\geq$ 60 bpm
Patient may resume LDK378 at $\downarrow$ 1 dose level with frequent monitoring  |
| Grade 4 (in patients taking a concomitant medication also known to cause bradycardia or a medication known to cause hypotension)                                | Omit dose until recovery to asymptomatic bradycardia or to a heart rate $\geq$ 60 bpm
If the concomitant medication can be adjusted or discontinued, resume LDK378 at $\downarrow$ 1 dose level with frequent monitoring   |
| Grade 4 (in patients who are not taking a concomitant medication also known to cause bradycardia or known to cause hypotension)                                 | Permanently discontinue patient from LDK378   |

| Worst toxicity (CTCAE 4.03 Grade)*  | Dose Modifications for LDK378 |
|--|--------------------------------------|
| 
* Common Terminology Criteria for Adverse Events (CTCAE) version 4.03. All dose modifications should be based on the worst preceding toxicity.
 
** If Grade 3 or 4 hyperbilirubinemia is due to the indirect (non-conjugated) component only, and hemolysis as the etiology has been ruled out as per institutional guidelines (e.g., review of peripheral blood smear and haptoglobin determination), then ↓ 1 dose level and continue treatment at the discretion of the Investigator.
 
***LFTs include albumin, ALT, AST, total bilirubin (fractionated if total bilirubin > 2.0 x ULN), alkaline phosphatase
 
**** Dose modifications apply to patients who experience diarrhea despite appropriate antidiarrheal medication. This medication should be started at the first sign of abdominal cramping, loose stools or overt diarrhea (see Section 6.3.2.5)
 
***** Dose modifications apply to patients who experience nausea and/or vomiting despite appropriate antiemetic medication. This medication should be started at the first sign of nausea and/or vomiting (see Section 6.3.2.6)
 |                                      |

